Executive Protocol Summary

ProstaCare Water Electrolysis System for the Treatment of Benign Prostatic Hyperplasia

CIP #: PC 1.0, Version: 2.1, Date: January 1, 2018

**Sponsored by: ProstaCare Singapore Pte. Ltd.
[name]**

This document is a confidential communication of **ProstaCare Singapore Pte. Ltd.**
Acceptance of this document constitutes the agreement by the recipient that
no unpublished information contained herein will be published or disclosed
without prior written approval from **ProstaCare Singapore Pte. Ltd.**

PROTOCOL SUMMARY

Study Title and Number	Prostafix Water Electrolysis System for the Treatment of Benign Prostatic Hyperplasia Prostafix Protocol # PC 1.0
Device Name	prostaFix Water Electrolysis System
Intended Use	The prostafix Water Electrolysis System is indicated for the treatment of lower urinary tract symptoms (LUTS) secondary to benign prostatic hyperplasia (BPH) in men > 45 years old with prostate volumes between 25 cm ³ and 55 cm ³ .
Purpose	To evaluate the safety and performance of the prostafix Water Electrolysis System in relieving symptoms of urinary outflow obstruction secondary to Benign Prostatic Hyperplasia (BPH).
Primary Objectives	Effectiveness: To demonstrate that BPH symptoms are improved by 6.5 points or more after use of ProstaFix as measured by the IPSS on all subjects at 3 months. Safety: To demonstrate that the Prostafix treatment does not cause unacceptable rates of serious adverse events (SAE) associated with use of the device.
Secondary Objectives	
 - To characterize changes in BPH symptoms, Qmax and PVR, sexual function, and quality of life (QOL) from baseline. - To characterize post-treatment recovery measuring treatment tolerability and medication requirements. - To measure durability at 6- and 12-months following treatment and up to 60 months after treatment for long-term durability. - To characterize prostate size and necrosis via MRI. - To characterize all adverse events (AEs) and technical observations on device performance.
Key Inclusion Criteria	
 - 45 years of age or older with a diagnosis of BPH, - International Prostate Symptom Score (IPSS) of 12 or greater, - Prostate volume between 25 cm³ and 55 cm³, - Uroflow with peak flow rate (Qmax) no greater than 13 ml/sec with a corresponding voided volume of at least 100 ml and a post void residual (PVR) of 250 ml or less. - Prostate length, width and height must be at least 3.2 cm, 3.5 cm and 2.5 cm, respectively
Key Exclusion Criteria	
 - Obstruction due to an enlarged middle lobe, central gland or significant transverse asymmetry, - Subjects on 5 alpha reductase inhibitors (5-ARI) (inclusion only if washed out prior to treatment), - Subjects on alpha blockers (inclusion only if washed-out before treatment), - Active urinary tract infection at time of treatment, - Interest in maintaining fertility, - Past history of urologic surgery or minimally invasive treatment for BPH, - History of or current medical conditions contraindicating elective urological procedures.
List of Investigators and Investigational Sites	
 - [name] [name], Singapore General Hospital - [name] [name], National University Hospital - [name], Urology BOP Consultant Urologists

1 STUDY DESIGN

1.1 Study Objectives

This study measures the safety and performance of the prostaFix Water Electrolysis System (ProstaCare), a minimally invasive treatment (MIT) that uses direct current to relieve symptoms of BPH. Benign Prostatic Hyperplasia (BPH) is prostate growth which may obstruct the urethra, inhibit urine flow and increase urinary symptoms.

1.2 Study Design

The study design is a prospective, multicenter, multinational, single-arm clinical investigation. A total of up to 50 subjects will be enrolled at 2-5 sites. Subject follow-up visits will be conducted at 2-day (if catheterized post procedure), 1 and 6 weeks, and 3 months to reach the primary endpoint visit analysis. The first few subjects will have fluoroscopic confirmation of electrodes placement before treatment, then fluoroscopy is optional. The first 10-15 subjects will have MRI studies at baseline, and the 1 week and 3-month follow-up visits to assess subject safety and treatment effect, then MRI is optional. Subject discomfort will be assessed throughout the treatment using VAS. Follow-up visits will assess BPH symptoms, uroflowmetry parameters, quality of life and adverse events.

Subjects will continue to attend follow-up visits at 6 months and 12 months after treatment to demonstrate treatment durability. After completion of their 12-month follow-up visit, subjects will have the option to continue study participation into the long-term follow-up phase with a yearly visit up to 5 years post treatment.

2 ENROLLMENT CRITERIA

2.1 Inclusion Criteria

Subjects must meet all of the inclusion criteria to participate in this study.

1. Subject must be a man of 45 years of age or older (BPH traditionally occurs in older men).
2. Subject must have an IPSS score of 12 or greater.
3. Subject must have a diagnosis of BPH in the medical records.
4. Subject must have an eligible uroflow with unadjusted or adjusted peak flow rate of equal to or less than 13 ml/sec with a corresponding:
 - a. voided volume of at least 100 ml, and
 - b. PVR of 250 ml or less.
5. Subject must have a prostate of 25-55 cc, inclusive as measured by ultrasound.
6. Subject must have prostatic sagittal length of 3.2 cm or greater, as measured by ultrasound.
7. Subject must have a prostatic transverse width of 3.5 cm or greater as measured by ultrasound.
8. Subject must have a prostatic anterior-posterior height of 2.5 cm or greater as measured by ultrasound.
9. Subject must have the ability to understand and consent to participate in this study.
10. Subject must be willing and able to participate in follow-up evaluations.

2.2 Exclusion Criteria

Subjects meeting any of the exclusion criteria listed at baseline will be excluded from participation.

1. Subject has obstruction due to an enlarged middle lobe or significant central gland of the prostate.
2. Subject has significant transverse asymmetry.
3. Subject has an implantable pacemaker or cardiac defibrillator.
4. Subject has a penile implant.
5. Subject has a history or current diagnosis of prostate cancer or bladder cancer.
6. Subject has an active urinary tract infection.
7. Subject has a neurogenic, decompensated or atonic bladder.
8. Subject has urethral strictures or muscle spasms that prevent insertion of the catheter.
9. Subject has bleeding disorders or anticoagulation meds unless anti-platelet meds has been discontinued for at least 7 days.
10. Subject has had previous rectal surgery other than hemorrhoidectomy.
11. Subject has had previous radical pelvic surgery or pelvic irradiation.
12. Subject is interested in maintaining fertility.
13. Subject has had previous surgical or minimally invasive procedure to treat symptomatic BPH.
14. Subject has alpha blocker use for the treatment of BPH within 14 days of treatment date.
15. Subject has 5ARI use within 3 months of treatment date.
16. History of medical, surgical or other conditions that, in the opinion of the investigator, would limit study participation.

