3 SCHEDULE OF EVENTS

Table 1: Tests and Evaluation Schedule with Visit Windows										
Parameter	Baseline -180 to 0 days	Baseline -60 to 0 days	Enroll - ment and Treatment (day 0)	As Indicated 2 day +3 /-1 days	1 week +/- 2 days	6 weeks +/- 7 days	3 months +/-14 days	6 months +/- 30 days	12 months +/-30 days	24, 36, 48, 60 months +/-30 days
Consent		X								
Medical Urological Hx		X								
Medication Review		X	X	X	X	X	X	X	X	X
IPSS		X			X	X	X	X	X	X
IIEF and MSHQ-EjD		X				X	X	X	X	
Uroflowmetry		X			X	X	X	X	X	
Post Void Residual		X			X	X	X	X	X	
Physical Exam +DRE		X								
PSA	X						X	X	X	
Urinalysis		X	X	If Indicated	If Indicated	If Indicated	If Indicated	If Indicated	If Indicated	
Urine Culture		X		If Indicated	If Indicated	If Indicated	If Indicated	If Indicated	If Indicated	
Ultrasound	X				If Indicated	In indicated	Optional	Optional	Optional	
Cystoscopy	X									
MRI		If Indicated			If Indicated		If Indicated			
Inclusion/Exclusion			X							
ProstaCare Therapy			X							
Fluoroscopy			If Indicated							
Pain VAS			X							
Voiding Trial			If Indicated	X	If Indicated					
Adverse Events			X	X	X	X	X	X	X	X
Device Deficiencies			X							
Risk Benefit Assessment							X		X	
Additional BPH Treatment Review					X	X	X	X	X	X

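### Exclusion 9 is wrong as written: it triggers on bleeding disorders or anticoagulants, its exception turns on anti-platelets, and its 7 days have no reference date

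*Protocol*

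**What the plan says.** Protocol section 2.2, item 9 excludes as follows: "Subject has bleeding disorders or anticoagulation meds unless anti-platelet meds has been discontinued for at least 7 days".

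Nothing else in the supplied protocol or SAP names bleeding disorders, anticoagulants or anti-platelets. The nearest related text is general:

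- The Key Exclusion Criteria in the Protocol Summary include "History of or current medical conditions contraindicating elective urological procedures".
- Section 2.2, item 16 includes "History of medical, surgical or other conditions that, in the opinion of the investigator, would limit study participation".

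Section 2.2 states that meeting any one exclusion at baseline is enough to exclude. In Table 1 (section 3), the "Inclusion/Exclusion" row is marked on day 0. The "Medication Review" row is marked at the baseline visit (up to 60 days before treatment), on day 0 and at every later visit.

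**The concern.** An exception should relax the condition that it is attached to. Here the condition is a bleeding disorder or an anticoagulant, and what relaxes it is the stopping of an anti-platelet. Stopping one drug removes neither a bleeding disorder nor the effect of a different drug still being taken. The class that the exception mentions is never itself excluded.

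Item 9 is the only explicit rule on these matters in the supplied text. The treatment requires a catheter to be inserted (item 8) and electrodes to be placed (section 1.2). The study is multinational, with 2-5 sites, so sites that read the item differently would make different eligibility decisions. A site that follows the words exactly could treat a man whom the rule was probably meant to keep out.

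**Working it through.** No arithmetic applies: the point rests on no rate, sample size or error probability. The check is to compare item 9 with its neighbours and then apply its words to particular men.

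**Comparison with neighbouring criteria**

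- Item 10: "Subject has had previous rectal surgery other than hemorrhoidectomy". The exempted operation belongs to the excluded class.
- Key Exclusion Criteria, alpha blockers: "Subjects on alpha blockers (inclusion only if washed-out before treatment". The washout belongs to the drug named.
- Key Exclusion Criteria, 5-ARI: "Subjects on 5 alpha reductase inhibitors (5-ARI) (inclusion only if washed out prior to treatment". The same holds.
- Items 14 and 15: each names one drug class, one interval (14 days for alpha blockers, 3 months for 5-ARI) and one anchor, the day of treatment.
- Item 9: the exception names a class absent from the trigger, and the 7 days have no anchor.

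**Item 9 applied literally**

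1. *A man currently on an anti-platelet, with no anticoagulant and no bleeding disorder.* The trigger is not met, so item 9 does not exclude him. The presence of an anti-platelet exception suggests that he was meant to be excluded.
2. *A man still on an anticoagulant who stopped an anti-platelet at least 7 days ago.* The trigger is met and so is the condition of the exception, so he is released. He stays excluded only if the reader confines the exception to anti-platelets.
3. *A man with a bleeding disorder who stopped an anti-platelet at least 7 days ago.* If *unless* governs both triggers, he is released. If it governs only the medication, he stays excluded. The sentence does not settle which.
4. *A man who has stopped an anticoagulant and takes no anti-platelet.* The item gives no interval for anticoagulants. Two sensible intents part here. If anticoagulant therapy always excludes, there is no washout route for him. If the 7-day stop was meant for blood-thinning drugs of either class, he may enter after 7 days.

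**Reference date**

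The exclusions are judged at baseline, and the baseline visit may fall up to 60 days before treatment. Seven days counted back from that visit would say nothing about drug use in the week before treatment. The day-0 eligibility check suggests that treatment is the intended anchor, but item 9 does not say so.

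**Effect on the statistics**

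The sample size in SAP section 2.3 rests on a mean change of 10 points, a standard deviation of 6, the goal of 6.5, one-sided 5% significance, 90% power and 10% attrition. None of these is taken from item 9. Rewording it also leaves unchanged the t-test in SAP section 2.2 and the exact binomial interval in SAP section 3.

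**The case against.** The strongest reply is that an experienced urologist would not read the item this way. An exception for stopped anti-platelets implies that anti-platelets belong to the excluded class, which makes the first case an unlikely admission. Confining the exception to the drugs it names is a natural reading and hardly a change to the text. The second and third cases also need a particular combination of circumstances, and a site willing to treat stopping one drug as clearing a different, continuing risk. The general contraindication criterion could catch a bleeding disorder, item 16 gives the investigator discretion, and medication is reviewed again on day 0.

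Much of this stands, and it is why the point is minor. It does not repair the rule. The general criteria name none of these drugs, item 16 depends on individual opinion, and the day-0 review has only item 9 as written to apply. A sympathetic reading still leaves two intents for a man who has stopped an anticoagulant, and it supplies no reference date.

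Three stronger inferences are tempting and unsupported:

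- *That the sponsor clearly meant anticoagulants to exclude without exception.* The text fits a 7-day stop for either class equally well.
- *That unsuitable men have been or will be treated.* The documents give no figures on use of these drugs or on how sites read the item.
- *That the full protocol has the same fault.* The supplied document is headed as an executive summary, so the fault is shown only there.

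**Conclusion.** Item 9 is wrong as written. This goes beyond missing detail: the stated rule, followed literally, leaves out men on an anti-platelet alone and can release men with a continuing anticoagulant or a bleeding disorder. The lack of a reference date for the 7 days is a second, smaller fault.

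The weight is minor. It is a matter of patient safety and of consistent eligibility decisions between sites, and its frequency cannot be estimated from the documents. Sample size, alpha, power and the planned analyses are unaffected.

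The conclusion assumes that the supplied wording is what sites use, and that anti-platelets were meant to be restricted, as the exception implies. It does not depend on which of the two intents for anticoagulants is right, because the text states neither.

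**What to change.** Check the wording in the full protocol first. If it is the same, replace item 9 with three separate rules:

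- **(a)** A bleeding disorder excludes, with no exception.
- **(b)** Anticoagulants, with the sponsor's clinicians choosing one form. Either use within a defined washout before the treatment date excludes (7 days if the present figure was meant to cover both classes), or any current anticoagulant therapy excludes with no washout route. The second form must make clear that stopping shortly before treatment does not qualify a man; otherwise someone who stopped the day before could enter.
- **(c)** Anti-platelet use in the 7 days before the treatment date excludes.

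The cost is one reworded criterion, issued in an amendment or clarification letter and applied at the existing day-0 medication review and eligibility check. A few more men may be excluded or have treatment delayed. The SAP needs no change.

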2 EFFICACY EVALUATION

2.1 Summary of Planned Analysis

The statistical analysis of efficacy is a within-subject analysis in which the significance of changes from baseline are assessed. No interim analyses are planned.

Initial analysis for the study objective will be performed when all subjects treated have completed their 3-month post-treatment visit and will be repeated at 6- and 12-month post-treatment visits. Analyses for this objective will be performed on an intention-to-treat basis, including all subjects treated under the protocol. Long-term analysis will be performed after completion of the 60-month visit for all remaining subjects.

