2.2 Hypothesis to be tested

The primary efficacy objective is to demonstrate that mean IPSS improvement (Δ IPSS) following treatment with the prostaFix Water Electrolysis System exceeds 6.5 points with 95% confidence.

The null and alternative hypotheses associated with this objective can be written as:

$$H_0: \mu_{\Delta IPSS} \leq 6.5 \text{ points}$$

$$H_A: \mu_{\Delta IPSS} > 6.5 \text{ points}$$

where $\mu_{\Delta IPSS}$ is the true underlying value of mean Δ IPSS following a treatment at the 3-month visit and 6.5 points is an objective performance goal (OPG). The objective is met at a given time point by rejection of the null hypothesis in a one-sided t-test at the 5% significance level.

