2.3 Sample Size Justification

The SAS proc power procedure was used to estimate the sample size required to reject the null hypothesis with 90% power at the one-sided 5% significance level in a paired t-test. The specific alternative hypothesis and standard deviation of the change in IPSS used in the calculation was derived from the feasibility study and other studies of devices for BPH. This suggested a mean change in IPSS of 10 points and a standard deviation of 6 points could be expected for this device.

Given these assumptions, a sample size of 27 subjects would provide adequate power to reject the null hypothesis. Allowing for a 10% attrition rate, a total of 30 subjects are required for this study. Actual number of subjects enrolled will range from 40-50.

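### The alpha-blocker washout is timed to treatment rather than to the baseline tests, so baseline IPSS, uroflow and PVR may be measured on drug

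*Protocol*

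**What the plan says.** Protocol 2.2, item 14, sets the washout: "Subject has alpha blocker use for the treatment of BPH within 14 days of treatment date". The Key Exclusion Criteria in the Protocol Summary tie it to the same event, without a duration: "Subjects on alpha blockers (inclusion only if washed-out before treatment".

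Table 1 (Protocol 3) marks IPSS, uroflowmetry and post-void residual in one pre-treatment column, "Baseline -60 to 0 days". The day 0 cells for all three are blank. The inclusion/exclusion check is marked on day 0 only. Medication is reviewed both at baseline and on day 0.

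Two entry criteria in Protocol 2.1 use these measurements: "Subject must have an IPSS score of 12 or greater" (item 2) and "peak flow rate of equal to or less than 13 ml/sec" (item 4). Neither says that the value must be obtained off drug.

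SAP 2.1 describes the efficacy analysis as "a within-subject analysis in which the significance of changes from baseline are assessed" and does not define baseline further. SAP 2.2 requires that the mean IPSS improvement "exceeds 6.5 points with 95% confidence". SAP 2.3 plans for "a mean change in IPSS of 10 points and a standard deviation of 6 points".

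**The concern.** The washout protects the treatment date, but the primary endpoint depends on the baseline measurement. Nothing in the supplied text requires the baseline tests to follow the washout or to be repeated after it.

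For a man scored on an alpha blocker and off it at 3 months, the change score is the device effect minus the drug effect he gave up. The study has one arm and a fixed goal, so no control group cancels the shift. The Qmax and PVR changes have the same problem. With 2 to 5 sites, the reported mean would depend partly on when each site took its baseline.

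A man tested on drug is also less likely to reach IPSS 12 or to stay at or below 13 ml/sec, so some men who would qualify off drug may be turned away.

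**Working it through.** **1. Is an on-drug baseline allowed?**

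Item 14 permits alpha-blocker use up to about day -15; whether day -14 itself is excluded is slightly ambiguous. The test window is days -60 to 0, which is 61 days. Days -60 to -15 make up 46 of them, and an on-drug test is allowed on each. For example, a man tested on drug on day -40 who stops on day -20 and is treated on day 0 breaks no rule.

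The gap is confined to alpha blockers. Item 15 requires 3 months off 5-ARIs, which is longer than the 60-day window, so those men are off drug at any of these tests.

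**2. The plan's own sample size**

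Inputs from SAP 2.2 and 2.3: mean change 10, goal 6.5, SD 6, one-sided 5%, power 90%, attrition 10%.

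- Difference to detect: 10 − 6.5 = 3.5.
- Power of the one-sample t-test: P(T > t₀.₉₅,ₙ₋₁), where T is non-central t with n − 1 degrees of freedom and non-centrality (3.5/6)√n.
- n = 26 gives 0.894 and n = 27 gives 0.904, so 27 reproduces. 27/0.9 = 30 also reproduces.
- Planned enrolment of 40–50 less 10% gives 36–45 evaluable men, with power 0.963–0.986.

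**3. Effect of on-drug baselines**

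Let f be the share of men measured on drug and off drug at 3 months, and d the IPSS points of drug effect each loses. Neither is in the documents; both are assumptions.

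- Mean loss = f × d, so the difference becomes 3.5 − f × d.
- Mixing affected and unaffected men raises the SD to √(36 + f(1 − f)d²).

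| f | d | Mean loss | Power at SD 6, n = 36 / 45 | Mixture SD | Power at mixture SD, n = 36 / 45 |
|---|---|---|---|---|---|
| 0 | – | 0 | 0.963 / 0.986 | 6 | 0.963 / 0.986 |
| 20% | 2 | 0.4 | 0.918 / 0.961 | 6.053 | 0.914 / 0.959 |
| 20% | 3 | 0.6 | 0.885 / 0.939 | 6.119 | 0.874 / 0.931 |
| 30% | 3 | 0.9 | 0.817 / 0.888 | 6.155 | 0.800 / 0.874 |
| 50% | 4 | 2.0 | 0.431 / 0.503 | 6.325 | 0.402 / 0.469 |

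The last row is an extreme case. At the SAP's minimum of 27 evaluable men, the 20% and 2-point case lowers power from 0.904 to 0.834 (SD 6).

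**4. How much loss the design can absorb (SD 6)**

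- Power stays at 90% or more up to a mean loss of 0.515 points (n = 36) or 0.841 (n = 45).
- Power stays at 80% or more up to 0.964 (n = 36) or 1.241 (n = 45). At 3 points per man these are 0.964/3 = 32% and 1.241/3 = 41% of men.

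**The case against.** The strongest reply is that the text permits on-drug baselines but does not show that any will occur. A site could test every alpha-blocker user after washout within the same window. The document is also an executive summary, and a fuller protocol may hold the missing rule. Both points stand, and they limit how firmly the size can be stated.

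The lead-in to Protocol 2.2 speaks of exclusion criteria at baseline, which might suggest that drug status is judged then. It does not close the gap: item 14 still counts back from treatment, and the eligibility check is marked on day 0.

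The understatement also needs the man to be off drug at 3 months, and no rule in the documents governs alpha blockers after treatment. Men with a strong drug response are the likeliest to fail the entry thresholds on drug, so those enrolled may lose less than assumed. If the studies behind the 10-point assumption timed their baselines in the same way, part of the loss is already counted. All three are fair and could make the true effect smaller than the table shows.

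Finally, the bias is conservative, and planned over-enrolment covers the mild case. That is true. It does not cover the moderate cases at 36 evaluable men, and it does nothing for the interpretation of the estimate or for the entry checks.

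**Conclusion.** The concern holds. The washout is anchored to the wrong event for a change-from-baseline endpoint, and a site that follows the protocol exactly can record an on-drug baseline.

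The consequence is an understated device effect and possible loss of power, not a false success. The mean understatement is the share affected times the drug effect per man. With 20–30% of men losing 2–3 points, it is 0.4 to 0.9 points. Power at 36–45 evaluable men is then 82–96% at SD 6, or 80–96% with the mixture SD, against 96–99% without the problem. These figures rest on assumed shares and drug effects and on affected men being off drug at 3 months. The gap itself follows directly from item 14 and Table 1. The change should be made, but the trial's validity does not hang on it.

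**What to change.** Amend Protocol 2.2 item 14 and Table 1. For men taking an alpha blocker, the IPSS, uroflow and PVR used for eligibility and baseline should be taken at least 14 days after the last dose and before treatment, or repeated then with the repeat values used as baseline.

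This fits the existing window. A last dose on day -60 allows testing from day -46 (−60 + 14). A last dose on day -15 allows day -1 (−15 + 14) or day 0 before treatment. The washout length and sample size do not change.

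The cost is protocol wording, plus later scheduling or one repeat questionnaire, uroflow and PVR for alpha-blocker users only. A man who stops close to day -15 has little slack, and a failed test on day -1 or 0 would cancel a booked procedure, so sites should stop the drug earlier where they can.

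If men have already been enrolled, the medication reviews at baseline and day 0 should let the sponsor count those affected. If a fuller protocol already has this rule, confirming it is enough.

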3 SAFETY EVALUATION

An overall summary of TEAEs will be made including the number and percentage of subjects with any TEAE, any severe TEAE, and any TEAE related to the device, any TEAE related to the procedure, serious TEAE and serious adverse device effect (SADE). A treatment-emergent adverse event (TEAE) is defined as an adverse event with a start date on or after the date of the treatment. In this summary, severe means CTC grade 3 or greater and related means possibly, probably or definitely related.

For the primary safety objective, the percentage of all subjects treated under the protocol who have been affected by one or more SADEs will be calculated along with the Clopper-Pearson exact binomial 95% confidence interval for this percentage. SADEs will also be summarized by term.

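### The 3-month 5-ARI washout is longer than the 60-day consent window, so a man who stops the drug to enter must stop before he can consent, with no adverse-event collection scheduled until day 0

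*Protocol*

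**What the plan says.** The Key Exclusion Criteria in the Protocol Summary do not bar 5-ARI users outright; they provide a route in: "inclusion only if washed out prior to treatment". Protocol section 2.2, item 15, sets the length of the drug-free period: "Subject has 5ARI use within 3 months of treatment date". Item 14 sets 14 days for alpha blockers.

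Table 1 in Protocol section 3 has two baseline columns. The earlier one, "Baseline -180 to 0 days", is marked only for PSA, ultrasound and cystoscopy. The later one, "Baseline -60 to 0 days", holds the only mark in the Consent row, and the first marks for urological history, medication review, IPSS, uroflowmetry and post-void residual. The Inclusion/Exclusion check is marked only at day 0, in the enrollment and treatment column. The first mark in the Adverse Events row is in that same column.

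SAP section 3 counts an event as treatment-emergent if it is "an adverse event with a start date on or after the date of the treatment". The efficacy analysis (SAP section 2.1) and the primary safety analysis (SAP section 3) cover treated subjects.

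**The concern.** The washout and the consent window are each stated plainly, but they cannot both be followed in the proper order. For a man taking a 5-ARI when he is first considered for the study, a site that keeps to Table 1 has him change medication for the study before he has agreed to take part. A site that takes consent first departs from Table 1.

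The stake is mainly subject protection. Stopping a drug for benign prostatic hyperplasia may be followed by worse symptoms or retention, and the schedule has no adverse-event collection in that period. There is also a reporting stake. In a single-arm trial judged against a fixed goal of 6.5 IPSS points, readers want to know how the treated group was reached, including how many men began a washout and did not get to treatment.

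**Working it through.** **The plan's own computed figure.** SAP section 2.3 gives 27 evaluable subjects. Inputs: mean change 10, goal 6.5, SD 6, one-sided 5% level, 90% power. The difference to detect is 10 − 6.5 = 3.5, and 3.5/6 = 0.583 SD. The exact noncentral-t calculation gives n = 27 with power 0.904, and 27/0.9 = 30 after 10% attrition. Both stated figures reproduce. Nothing below depends on them.

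**Inputs for the timing check.**
- Drug-free period before treatment: 3 months (Protocol 2.2, item 15).
- Earliest permitted consent: day −60 (Table 1, Consent row).
- First scheduled adverse-event collection: day 0 (Table 1, Adverse Events row).
- Comparison: alpha-blocker-free period of 14 days (Protocol 2.2, item 14).

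**Length of 3 months.** Counting back 3 calendar months from every treatment date in a four-year span gives 89 to 92 days.

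**Gap before consent.** Gap = drug-free days − days from consent to treatment. It is smallest when consent is taken as early as allowed, at day −60:
- shortest calendar case: 89 − 60 = 29 days;
- longest calendar case: 92 − 60 = 32 days;
- 3 months taken as 90 days: 90 − 60 = 30 days;
- 3 months taken as 12 weeks (84 days): 84 − 60 = 24 days.

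No reasonable reading of 3 months closes the gap. Later consent widens it: with consent on day 0, the whole 89 to 92 days come first. Seen from the other side, a man who consents on day −60 and stops that day has been off drug for only 60 days at treatment, and item 15 excludes him.

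**Alpha blockers.** 60 − 14 = 46 days to spare. Consent can come before this washout within Table 1, so there is no conflict.

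**Period without scheduled adverse-event collection.** This runs from stopping the drug to day 0, which is 89 to 92 days. With the earliest consent it divides into 29 to 32 days before consent and 60 days after it (29 + 60 = 89; 32 + 60 = 92).

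**The case against.** The strongest reply is that the protocol supplied is an executive summary. It has no section on consent procedure, screening or adverse-event reporting, and a fuller document may cover them. This stands against one stronger reading. A reader might infer that men who drop out during washout leave no record at all. That would be an inference from silence: the supplied text shows no screening log, but it does not show that none exists. The reply does not remove the conflict between item 15 and the Consent row, since both are explicit.

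Second, no passage says who stops the drug or when, and item 15 can be read as a condition on past use. Men already off a 5-ARI for 3 months for other reasons are indeed unaffected. But the summary speaks of washout as a way into the study, and the conflict arises for the men who take that route.

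Third, the urological history and medication review in the later baseline column might pick up some earlier events, such as retention, in men who reach consent. That is fair, though it would be history and not adverse-event reporting.

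Fourth, a reader might extend the point to alpha blockers or to the tests in the earlier baseline column. Neither extension is supported. The 14 days fit inside the window; late consent could still put that washout first, but the schedule does not force it. The earlier column can be read as a look-back for tests already done in routine care.

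Fifth, a reader might infer that the primary results are biased. The documents do not show this. The primary safety measure concerns serious device effects in treated subjects, which cannot occur before the device is used. Any selection of men who tolerate withdrawal comes from the washout criterion itself and would remain under any consent schedule.

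**Conclusion.** The conflict holds and should be corrected. For every man who stops a 5-ARI in order to enter, following the plan as written puts a study-driven medication change at least 29 to 32 days before the earliest permitted consent (24 days if 3 months means 12 weeks). It also leaves the whole washout, including up to 60 days after consent, without scheduled adverse-event collection.

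This rests on three assumptions: that the summary's washout wording means stopping in order to enter, that the single Consent mark defines when consent may be taken, and that day 0 is the treatment date. The documents do not say how many men are affected; it could be few or none. Confidence is high for the timing conflict and for the start of scheduled adverse-event collection. It is lower for unrecorded losses, because the full protocol was not available. The IPSS test, the SADE analysis and the sample size are untouched.

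**What to change.** 1. Reconcile the Protocol Summary, section 2.2 item 15 and Table 1 so that consent can, and must, come before any medication change made for the study. One way is to allow Consent in the −180 to 0 day column, with tests from routine care still usable. The length of the washout is for the sponsor and investigators to settle; no view is taken on it here.
2. Start the Adverse Events row at consent.
3. List pre-treatment events, and men who leave during washout with their reasons, separately from TEAEs. If a screening log already exists in a fuller document, refer to it; if not, add one. The SAP's TEAE definition can stay as it is.

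The cost is a protocol amendment to Table 1 and, if needed, a log. Some men will consent earlier, and more consented men will be counted as screen failures. No extra subjects or procedures are needed. The change makes losses during washout visible; it does not remove the selection that a washout brings.
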